14.4.2 The CTR responsibilities

Following the initial report, all SAEs should be followed up to resolution wherever possible, and further information may be requested by the CTR. Follow up information must be provided on a new SAE form.

The CTR should continue reporting SAEs until 7days after the participant completes the trial protocol. Serious adverse reactions should continue to be reported until the end of follow up.

Once an SAE is received at the CTR, it will be evaluated by staff at the CTR and sent to the Chief Investigator (or their delegate) for an assessment of expectedness.

Investigator reports of suspected SARs will be reviewed immediately and those that are identified as SUSARs are reported to the MHRA, Main Ethics Committee.

14.5 SUSAR reporting

The Newcastle upon Tyne Hospitals NHS Foundation Trust is undertaking the duties of trial Sponsor and has delegated to the CTR the responsibility for reporting SUSARs and other SARs to the regulatory authorities (NCAs and relevant ethics committees) as follows:

SUSARs which are fatal or life-threatening must be reported to the MHRA and REC within 7 calendar days of receipt at the CTR.

SUSARs that are not fatal or life-threatening must be reported to the MHRA and REC within 15 days of receipt at the CTR.

Canolfan

If report is incomplete then additional follow-up information should be reported within a further 8 calendar days of submitting the initial report, for all fatal and non-fatal, life-threatening and non-life threatening.

Any additional, relevant information must be reported within a further 15 days.

14.6 Unblinding for the purposes of SUSAR reporting

VESPER is an unblinded trial, this section, therefore is not applicable.

14.7 **Safety Reports**

A list of all SARs (expected and unexpected) will be reported annually to the MHRA REC, trial sponsor in the form of a Development Safety Update Report (DSUR). This report must be submitted within 60 days of the anniversary of the MHRA CTA approval date.

The CTR will report a list of all SARs (expected and unexpected) and any other safety recommendations to all PIs annually throughout the course of the trial. This frequency may be reviewed and amended as necessary. This reporting will be done via the Investigator safety report (ISR).

Insert details of any specific reporting of SAEs performed by the drug company, and/or production and submission of the trial specific DSUR.

14.8 **Contraception and pregnancy**

14.8.1 Contraception

The oral antibiotic Trimethoprim, used in this trial has a demonstrated or suspected human teratogenicity/fetotoxicity. The oral antibiotic Nitrofurantoin, used in this trial has demonstrated a risk of neonatal haemolysis when used in late pregnancy. The oral antibiotic Cefalexin is considered safe to use in pregnancy. Intravesical treatments are generally avoided during pregnancy due to the need for repeated bladder catheterisation. WOCBP entering into this trial must agree to use a highly effective method of contraception preferably with low user dependency for at least one month after the last dose of the trial treatment. A highly effective method of contraception is considered as having a failure rate of less than 1% per. Some acceptable contraception methods are listed below;

 combined (oestrogen and progestogen containing) hormonal contraception associated with inhibition of ovulation:

VESPER

- \circ oral
- o intravaginal
- o transdermal
- progestogen-only hormonal contraception associated with inhibition of ovulation
 - o oral
 - o injectable
 - implantable*
- intrauterine device (IUD)*
- intrauterine hormone-releasing system (IUS)*
- bilateral tubal occlusion*
- vasectomised partner*
- sexual abstinence defined as refraining from heterosexual intercourse during the entire period of risk associated with the trial treatments.

N.B. periodic abstinence (calendar, symptothermal, post-ovulation methods), withdrawal (coitus interruptus), spermicides only, and lactational amenorrhoea method (LAM) are not acceptable methods of contraception.

*These contraception methods are considered to be low user dependency.

14.8.2 Pregnancy reporting whilst participating in the trial

Pregnancy, or the pregnancy of a partner occurring whilst participating in the trial, is not considered an SAE, however, a congenital anomaly or birth defect is. Other cases (e.g. termination of pregnancy without information on congenital malformation, and reports of pregnancy exposure without outcome data) should not normally be reported as such. When pregnancy occurs in a trial, either in a female participant or the female partner of a male participant, this should be followed up until at least the end of pregnancy, whether that is a live birth, termination of pregnancy etc. Without follow-up

of the pregnancy, it would not be possible for the CTR to know if a congenital anomaly or birth defect occurred, and therefore if there was an SAE that must be included in the safety evaluation of the IMP.

Information on a pregnancy in a VESPER trial participant will be captured by sites on the CTR Pregnancy Report Form (PRF) supplied to sites by the CTR. The PRF should be completed by the trial site within 7 days of becoming aware of the pregnancy and then emailed to the CTR ([contact]). Any participant identified as being pregnant whilst on the trial will, under the supervision of the principal investigator at site, have their trial treatment stopped. The site, on becoming aware of the pregnancy, will also complete a withdrawal form. The participant can choose to continue to provide follow-up data and or provide samples even though their trial treatment will be stopped.

VESPER sites must report pregnancy occurring within SAE reporting periods as stipulated in the trial protocol (from time of signature of informed consent, throughout the treatment period up to, and including 7 days after the participant completes the trial protocol). Congenital anomalies or birth defects are considered an SAE and so these events must also be reported to the CTR on a trial-specific SAE form. Congenital anomalies or birth defects related to the IMP and unexpected with respect to the IMP Reference Safety Information (RSI) must be submitted by the CTR within expedited SUSAR time frames (7 or 15 days) to the MHRA, relevant REC.

14.9 Urgent Safety Measures (USMs)

An urgent safety measure is an action that the Sponsor, Chief Investigator or Principal Investigator may carry out in order to protect the subjects of a trial against any immediate hazard to their health or safety. The principal investigator or delegated team member at the VESPER recruiting sites must notify the CTR as soon as an USM has been implemented by emailing and marking as urgent: [contact]. The trial manager at the CTR will notify the MHRA and Research Ethics Committee of any USMs immediately by telephone, and in any event within 3 days of being made aware of the USM, in writing, that such a measure has been taken. USMs reported to the CTR will be handled according to CTR processes.

15 Statistical considerations

15.1 Randomisation

Participants will be individually allocated in a 1:3:3 ratio to one of the three trial arms: (1) intravesical gentamicin, (2) intravesical GAG replacement or (3) oral antibiotic prophylaxis for up to 6 months. The covariate-adaptive randomisation procedure following the Pocock and Simon's range method_will be used to minimise the imbalance of key covariates with an 80% random element applied to reduce the risk of subversion. These key minimisation factors are:

- prior frequency of UTI (<= 4 episodes per year or > 4 episodes per year)
- menopausal status (pre-menopausal or menopausal/post-menopausal)

Following randomisation, those in the oral antibiotics arm will be issued with a prescription. For those in the intravesical arms an appointment will be arranged for the participant to come back to clinic for their first instillation.

Participants can be re-randomised to a different prophylactic regime due to lack of efficacy or incidence of predefined adverse events. These include i.) relapse with at least two episodes of UTI occurring in the 6-month treatment period in line with currently accepted definitions of recurrent UTI; ii.) intolerance of side effects of prophylactic antibiotic. In this event, participants will be re-randomised 1:1 between the two remaining allocations. Re-randomisation will be based on block randomisation with no stratification. An individual not otherwise involved with the study will produce the final re-randomisation schedule. The randomisation procedure will be implemented via a webbased remote system (TMS2 - available 24 hours a day) that bult in-house CTR Information Systems and Technology Solutions team with telephone back-up as described in Section 9.5.2. Full details will be provided in a separate randomisation protocol.

15.2 Blinding

The VESPER trial does not use blinding of participants or clinicians. However, the statisticians who perform the primary analysis blind to allocation.

15.3 Sample size

We aim to recruit 412 participants over 21 months and follow them up for a fixed 12-month period (62 in the oral comparator arm and 175 in both intravesical experimental arms). We are primarily interested in comparisons of each intravesical prophylaxis against standard care and then a head-to-head comparison of intravesical prophylaxes.

Two sets of comparisons are powered. The first set compares each intravesical prophylaxis arm to the second-line prophylactic oral antibiotics arm to detect a difference in the UTI rate of 1 (assumed UTI rate of 2 from previous studies³). This is calculated based on 90% power, and two-sided alpha of 0.05 (no multiplicity adjustment as comparisons is considered independent). This comparison requires 62 participants in each arm (1:1:1 ratio). The second set is to detect a difference in the UTI rate between the intravesical arms. This is calculated based on 90% power, 5% two-sided alpha (no adjustment as we are making this comparison as part of a fixed sequence. That is, we will only compare the intravesical prophylaxis arms head-to-head if both are superior to the second-line prophylactic oral antibiotics arm), with target effect size of 30% (i.e. a relative difference of 30% between intravesical arms, with an assumed UTI rate of one in one of the intravesical arms). This comparison requires 175 in each intravesical arms and hence 1:3:3 ratio.

Target differences between oral and intravesical treatments are based on PPI work. In line with previous studies³ the PPI group for VESPER overwhelmingly stated that any intravesical treatment demonstrating a reduction in UTI frequency of 1 episode per year greater than oral antibiotic tablets would be considered superior. Target differences between intravesical treatments are based on our clinician survey administered via UKCS which revealed that the majority of clinicians felt that for one intravesical treatment to be considered superior to another there would need to be a 30% or greater difference in efficacy. This sample size is further inflated to account for a 15% drop-out (as observed in the ALTAR trial³).

Although we are proposing a SMART design, our primary interest is the marginal effect of the initial prophylaxis, the comparison of each treatment sequence is considered exploratory and hence the SMART design has no impact on our required sample size.

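### The gentamicin versus GAG comparison is stated at 90% power, but 175 women per arm gives about 80% on the protocol's own inputs

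*Protocol*

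**What the plan says.** Section 15.3 of the protocol powers two sets of comparisons. The first sets each intravesical arm against oral antibiotics (UTI rate 2, difference 1) and needs 62 per arm. The second compares the two intravesical arms. For the second it says: "This is calculated based on 90% power, 5% two-sided alpha". The effect is "a relative difference of 30% between intravesical arms, with an assumed UTI rate of one in one of the intravesical arms", and alpha is left unadjusted because the test sits in a fixed sequence after both comparisons with oral treatment. The conclusion is "This comparison requires 175 in each intravesical arms and hence 1:3:3 ratio".

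The section later adds: "This sample size is further inflated to account for a 15% drop-out". The recruitment target is 412 = 62 + 175 + 175, so 175 is the number recruited per intravesical arm, after the drop-out allowance. Section 16.1 plans a Poisson or negative binomial model. Section 15.3 names no formula and no dispersion value.

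**The concern.** The stated power, effect size, drop-out and sample size do not fit together. With 175 recruited and 15% lost, 148.75 women per arm remain analysable. That is too few for 90% power to separate rates of 1 and 0.7, even under the favourable assumption of pure Poisson variation.

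The head-to-head comparison is the reason for the 1:3:3 allocation and for most of the recruitment. The 30% margin comes from the clinician survey cited in the same section as the threshold for calling one intravesical treatment superior. If power is overstated, a non-significant result will look like stronger evidence that gentamicin and GAG are similar than it is.

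**Working it through.** **Inputs, all from section 15.3:** two-sided alpha 0.05 (z = 1.960); power 90% (z = 1.282); rates 1 and 0.7, the plain reading of a 30% relative difference from a rate of one; equal arms; drop-out 15%. Exposure is taken as one unit, so that the rate is the expected count per woman.

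**Formula** for two Poisson rates, per arm: n = (z_alpha/2 + z_power)² × (λ1 + λ2) / (λ1 − λ2)², then divide by 0.85.

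**Trying to reproduce 175**

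- At 90% power: (1.960 + 1.282)² × 1.7 / 0.09 = 10.507 × 18.889 = 198.5 analysable; 198.5/0.85 = 233.5 recruited. This does not match.
- At 80% power: (1.960 + 0.842)² × 1.7 / 0.09 = 7.849 × 18.889 = 148.3 analysable; 148.3/0.85 = 174.4, rounded up to 175. This matches.

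| Method | 90%: analysable | 90%: recruited | 80%: analysable | 80%: recruited |
|---|---|---|---|---|
| Rate difference | 198.5 | 233.5 | 148.3 | 174.4 |
| Log rate ratio | 200.6 | 236.0 | 149.8 | 176.3 |
| Square root | 196.9 | 231.6 | 147.1 | 173.1 |

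All three methods put 175 within two women of the 80% figure and more than 55 below the 90% figure.

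**Power that 175 recruited delivers**

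- Analysable: 175 × 0.85 = 148.75. Then 0.3/√(1.7/148.75) = 2.806, and 2.806 − 1.960 = 0.846, which gives power of 80.1%. The log scale gives 79.7%. Poisson simulation at 149 per arm gives 80.3%.
- No drop-out at all: 0.3/√(1.7/175) = 3.044, which gives 86.1% (85.7% on the log scale).
- Detectable reduction at 90% power with about 149 per arm: 34.2% (rate difference) to 34.5% (log scale).

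**Sensitivity to what the section leaves open (148.75 analysable per arm unless stated)**

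| Assumption | Power |
|---|---|
| Drop-outs supply half their follow-up (161.9 effective) | 83% |
| 30% read as 1 v 1.3 | 67% |
| 30% read as 1 v 1.43 | 92% |
| 1 v 0.7, negative binomial dispersion 0.25 (assumed) | 72% |
| 1 v 0.7, negative binomial dispersion 0.5 (assumed) | 65% |
| 1 v 0.7, negative binomial dispersion 1 (assumed) | 54% |

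The negative binomial rows use the log-scale variance (1/λ1 + 1/λ2 + 2k)/n, where k is the dispersion.

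**The case against.** Four points can be made for the protocol.

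1. **The method is not stated.** The formula that yields 175 at 80% power does not yield the oral arm's 62: for 2 v 1 at 90% it gives 31.5 analysable, or 37 recruited. The authors may have used another method. A formula that takes the null variance at the reference rate needs 179 per arm before drop-out, close to 175, and gives 89.4% power at 175. It reaches that only by leaving out the drop-out the section says is included. With drop-out it needs 211, and 148.75 analysable gives 84%. What stands is that the use of 80% is an inference from a numerical match. The shortfall does not depend on it.

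2. **The direction of the 30% is open.** If the arm with rate one is the better arm, the other has 1/0.7 = 1.43, and power is 92%. This is the one reading found that supports 90% after drop-out. It needs 164 to 166 recruited, so it does not reproduce 175. It also puts the worse arm only 0.57 below the oral rate of 2, where the first comparison assumes a difference of 1. If it was intended, the section must say so.

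3. **Drop-outs are not a total loss.** A rate model can use partial exposure, and section 15.4 plans multiple imputation. Half follow-up from drop-outs raises power to about 83%. Imputation does not supply events that were never observed.

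4. **The consequence is limited.** The comparison is tested only if both intravesical arms beat oral treatment, and estimates will carry confidence intervals. That is fair: the error is in a stated design property, and the analysis itself is unaffected.

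**Conclusion.** The concern holds. On the plain reading (1 v 0.7, Poisson variance, two-sided 5%, 15% drop-out), 175 recruited per arm gives about 80% power, not 90%. Allowing for partial follow-up or for the reference-variance formula, the range is about 80 to 84%; with no losses it is 86%. On the plain reading the false-negative risk is about 20% against a stated 10%.

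The result rests on reading the 30% as a reduction from one and on no overdispersion. Overdispersion would only lower the figure. That 80% was used where 90% is written is the likeliest explanation, but it is not proved.

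**What to change.** In section 15.3, for the head-to-head comparison:

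- Replace 90% with 80% power. Alternatively, keep 90% and restate the detectable relative reduction as about 34 to 35%. The first is the better choice, because the 30% margin comes from the clinician survey.
- State both assumed rates and the formula used.
- State that 175 is after 15% drop-out, leaving about 149 analysable per arm.
- Give the power under at least one stated overdispersion value.

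Any statistical analysis plan should carry the same figures. The change is wording only and leaves the sample size at 412; its cost is a less favourable stated power. For scale, keeping both 90% and 30% would need 199/0.85 = 234.1, so 235 per intravesical arm, and 2 × 235 + 62 = 532 in total. That is not proposed here. The correction should be made before any outcome data are analysed.

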16.1 Main analysis

Descriptive statistics will be summarised using frequencies and percentages, means and standard deviations, or medians and interquartile ranges as appropriate. Recruitment, retention, and other trial processes (e.g. adherence to allocation) will be reported both overall, by arm, and disaggregated by site, menopausal status, previous UTI frequency, and previous type of failed treatment.

The primary analysis will be an intention to treat, including all randomised participants regardless of adherence or discontinuation of the initial treatment allocation or initiation of the subsequent treatment.

For the clinical-effectiveness primary outcome (rate of symptomatic, antibiotic-treated UTI, selfreported by participants from randomisation to the 6-month treatment period (verified from medical

Canolfan

records)), a Poisson/negative binomial regression model will be fitted to estimate incidence rate ratios, including fixed effects for allocation, covariate factors used in randomisation (prior frequency of UTI and menopausal status) and random effects to model heterogeneity between sites. Regression analysis results will be presented as point estimates with confidence intervals and p-values. The primary estimand for VESPER is below:

Primary clinical question: In women who fail first-line preventative treatment for rUTI, does the strategy to initially prescribe intravesical treatments result in a greater reduction in the rate of symptomatic UTIs over the subsequent 6 months compared to the current guideline-recommended second-line prophylactic antibiotic therapy?

The estimand is described by the following attributes:

- Population: women aged >16years with recurrent uncomplicated UTI who have failed firstline treatments requiring second-line prophylactic treatment and able to receive intravesical treatments and take second-line oral antibiotic prophylaxis.
- **Endpoint**: rate of symptomatic UTIs from randomisation to 6-months. •
- **Treatment condition**: The intravesical treatments and second-line oral antibiotic prophylaxis, regardless of adherence or discontinuation of the initial treatment allocation or initiation of the subsequent treatment (via re-randomisation) (treatment policy strategy);
- Remaining intercurrent events: Treatment adherence or discontinuation or initiation of the subsequent treatment are covered by previous attribute.

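### Section 15.3 gives the UTI rates no time unit and never converts the yearly target to the 6-month endpoint, so the stated 90% power cannot be relied on for both comparisons

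*Protocol*

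**What the plan says.** Protocol section 15.3 powers two sets of comparisons.

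- Each intravesical arm against oral antibiotics: the aim is "to detect a difference in the UTI rate of 1 (assumed UTI rate of 2 from previous studies"), at 90% power and two-sided 5%, and "This comparison requires 62 participants in each arm (1:1:1 ratio").
- The two intravesical arms against each other, tested only if both beat oral treatment: 90% power, two-sided 5%, and "a relative difference of 30% between intravesical arms, with an assumed UTI rate of one in one of the intravesical arms". The stated requirement is 175 per arm, which is the reason given for the 1:3:3 ratio.

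No time unit is attached to 2, 1 or the 30% difference. The same section bases the first target on patient input: "any intravesical treatment demonstrating a reduction in UTI frequency of 1 episode per year greater than oral antibiotic tablets would be considered superior". Section 25 repeats the figure of one episode per year. The endpoint in the section 16.1 estimand is the "rate of symptomatic UTIs from randomisation to 6-months", and section 5.3 uses the same 6-month window. Section 15.3 also says that the sample size allows for 15% drop-out. It gives no dispersion parameter, although section 16.1 permits a Poisson or a negative binomial model.

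**The concern.** Power for a count endpoint depends on the expected number of events per woman in the counting window. A rate of 1 means one expected event if it is per 6 months and half an event if it is per year. Because the target is expressed per year and the endpoint covers half a year, a conversion is needed, and none appears anywhere in the protocol.

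Two things are at stake. The head-to-head comparison drives the allocation ratio and most of the 412 participants; if its real power is far below 90%, a null result there would say little. And a reader cannot tell whether the first comparison is sized for the difference that patients named or for twice that difference. This is not detail left to the SAP, because section 15.3 itself fixes the numbers, the power and the target differences.

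**Working it through.** **Inputs** (section 15.3): two-sided 5%; 90% power; rates 2 v 1 and 1 v 0.7; 62, 175 and 175 randomised; 15% drop-out. Since 62 + 175 + 175 = 412, nothing is added beyond the per-arm figures, so the evaluable numbers are 0.85 × 62 = 52.7 and 0.85 × 175 = 148.75.

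**Formulas**, with m the expected count per woman:

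- Rate difference: n = A(m1 + m2)/(m1 − m2)²
- Log rate ratio: n = A(1/m1 + 1/m2)/[ln(m1/m2)]²
- A = (1.960 + 1.282)² = 10.507 for 90% power; A = 7.849 for 80%
- Power = Φ(effect/SE − 1.960), with Poisson variances

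**1. Reproducing the stated sizes**

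| Comparison | Expected counts | Power | Evaluable per arm | ÷ 0.85 |
|---|---|---|---|---|
| First, full unit | 2 v 1 | 90% | 10.507 × 3/1 = 31.5; log 32.8 | 37–39 |
| First, half unit | 1 v 0.5 | 90% | 10.507 × 1.5/0.25 = 63.0; log 65.6 | 74–77 |
| Head-to-head, full unit | 1 v 0.7 | 90% | 10.507 × 1.7/0.09 = 198.5; log 200.6 | 233–236 |
| Head-to-head, full unit | 1 v 0.7 | 80% | 7.849 × 1.7/0.09 = 148.3; log 149.8 | 174–176 |
| Head-to-head, half unit | 0.5 v 0.35 | 90% | 10.507 × 0.85/0.0225 = 396.9; log 401.2 | 467–472 |

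The 62 fits annual rates over half a year without drop-out inflation (a square-root formula gives 61.2). It also fits 2 v 1 over a full unit with a negative binomial dispersion k. Solving 62 = A(1.5 + 2k)/0.4805 gives k ≈ 0.67, or k ≈ 0.45 if 52.7 are evaluable. The 175 fits 1 v 0.7 over a full unit at 80% power with drop-out, not at the stated 90%.

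**2. If the rates are annual (6-month counts 1.0 v 0.5 and 0.5 v 0.35)**

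- First comparison, difference scale: 0.5/√(1/52.7 + 0.5/148.75) = 3.345, power 92%. Log scale: 0.693/√(1/52.7 + 1/74.4) = 3.85, power 97%.
- Head-to-head: 0.15/√(0.85/148.75) = 1.984, power 51.0%; log scale 50.6%. With all 175 evaluable, 57–58%.
- If rate 1 is the lower arm, with 148.75 evaluable: 0.5 v 0.65 (1.3 per year) gives 40%, and 0.5 v 0.714 (1/0.7 = 1.43 per year) gives 66%. With all 175 these become about 46% and 73%.
- The reduction from 0.5 detectable at 80% power with about 149 per arm is about 41%.
- With assumed dispersion 0.5 or 1, the 51% becomes 44% or 38%, and the first comparison has 79–90% at 0.5.

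**3. Separating the two causes.** Over a full unit, 0.3/√(1.7/148.75) = 2.806 gives 80% (86% with no loss). Had 90% truly been met over a full unit, halving exposure alone would give Φ(3.2415/√2 − 1.960) = Φ(0.332) = 63%.

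**4. If the rates are per 6 months**

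- Head-to-head for 1 v 0.7: about 80%. The direction matters here too: 1 v 1.3 gives 0.3/√(2.3/148.75) = 2.413, about 67%, and 1 v 1.43 gives 0.4286/√(2.4286/148.75) = 3.354, about 92%.
- First comparison for 2 v 1: above 99%. But 1 per 6 months is 2 per year. The patient threshold of 1 per year is 2.0 v 1.5: 0.5/√(2/52.7 + 1.5/148.75) = 2.281, power 63%; log scale 68%. With dispersion 0.5, 37–42%.

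**The case against.** The strongest defence is that the comparison in the primary estimand is sound on the more natural reading. The patient threshold is per year, 62 is close to what annual rates over half a year require, and 1.0 v 0.5 with 53 v 149 evaluable has 92–97% Poisson power. The head-to-head is a gated second step. On the 6-month reading, the literal claim of 90% power for a difference of 1 is also met. All of this stands, and it limits the point: on the annual reading the damage is confined to the head-to-head, and on the 6-month reading what fails for the first comparison is its match to the cited patient threshold.

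It is also fair that 149 evaluable treats the 15% as contributing nothing, whereas sections 15.4 and 15.7 keep all eligible randomised women, with multiple imputation. Imputation does not create information, but partial follow-up does, so the figure lies between 51% and 57–58%.

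Two stronger readings are tempting. A reader might infer that the missing unit by itself brings the head-to-head down to 51%. The figures do not support that: 175 gives about 80% for 1 v 0.7 even over a full unit, and halving exposure from a true 90% would leave about 63%. A reader might also infer that the two sample sizes were calculated on different time bases. That is possible but not established, since 62 can also arise from overdispersion that the protocol does not state.

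**Conclusion.** The point holds as an unresolved unit that leaves a stated design property unmet or unsupported on either reading. With annual rates, head-to-head power is about 51% for 1 v 0.7 (40–66% across directions of the 30% when rate 1 is the lower arm, at 149 evaluable), and no variant examined reaches 90%. With 6-month rates, the first comparison targets twice the patient threshold and has about 63–68% power for the threshold itself, while the head-to-head has about 80% for 1 v 0.7. Only the variant with 1.43 in the worse arm reaches 90% there.

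The documents do not support saying that the trial as a whole is underpowered, or fixing on one power figure, because the unit, the direction of the 30% and the dispersion are all unstated. The figures assume Poisson counts, 15% contributing no data unless noted, and no gain from covariate adjustment. They are for the head-to-head test once it is reached in the fixed sequence. Dispersion values of 0.5 and 1 are assumptions; any overdispersion lowers every figure. Confidence is high on the missing conversion and lower on any single power value.

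**What to change.** In section 15.3, state the time unit of every rate, the expected 6-month count in each arm, which intravesical arm carries rate 1 and how the 30% is applied, whether 62 and 175 already include the 15% drop-out, and any dispersion assumed. Then restate power for both comparisons on that basis.

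- If the rates are annual, give the actual head-to-head power for a 30% difference, or the detectable reduction (about 41% at 80% power under the assumptions above).
- If they are per 6 months, say that the powered difference for the first comparison is 2 episodes per year, and give the power for 1 per year.
- In either case, reconcile 175 with the stated 90%.

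The cost is protocol and SAP wording. N stays at 412; the stated power becomes less favourable.
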